**The Effects of Two Different Electrical Stimulation Methods on the Pain Intensity of
the Patients Who Had Undergone Abdominal Surgery With a Midline Incision:
Randomized Controlled Clinical Trial**

[name]

[name], Professor

Document Date: May 1, 2015

The effects of two different electrical stimulation methods on the pain intensity of the patients who had undergone abdominal surgery with a midline incision: Randomized Controlled Clinical Trial

**[name]
[name]**

This study was conducted as a randomized controlled trial. The primary outcome measures were the effects of TENS and TAES on pain and analgesic drug consumption in patients who had undergone abdominal surgery with a midline incision. Secondary outcome measures were the effects of TENS and TAES use on respiratory functions, vital signs, nausea and vomiting status, dizziness, antiemetic drug consumption, and saturation

Study setting

This study was conducted at the Department of General Surgery of the Gülhane Training and Research Hospital in Ankara, Turkey between May 2015 and November 2016.

Participants

The population consisted of General Surgery patients who underwent planned abdominal surgery with a midline incision between May 2015 and November 2016. The study sample comprised patients who underwent abdominal surgery with a midline incision due to problems related to colorectal cancer and stomach cancer. The principal investigator evaluated patients awaiting abdominal surgery with a midline incision in the hospital room the day before the surgery to ensure that the patients qualified for the study in accordance with the eligibility criteria.

Inclusion criteria

Patients who had an American Society of Anesthesiologists (ASA) score of I-II, were aged over 18 years, who could read and write Turkish, who were scheduled to undergo elective abdominal surgery with a midline incision for a diagnosis of stomach or colorectal cancer, and without any impairment of vision, hearing or speech were included in the study.

Exclusion criteria

Patients who had a pacemaker, whose skin integrity around the incision was degraded, had a cognitive disorder, had a history of chronic pain, or were suffering from neurological, renal, cardiac or pulmonary disorders that could affect the test results, and patients with an opioid addiction, those who had previously undergone electrical stimulation treatment, morbidly obese subjects and patients using

psychoactive drugs were excluded.

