surgery. 4 electrodes were placed 2-3 cm lateral to the incision of the patients at the 30th minute and 2, 18, 22, 42, and 46th hours after the surgery and electrical stimulation was implemented at varying frequencies of 2-100 Hz for 30 minutes, at a maximum current intensity of 12 milliamperes that would not bother the patient or create muscle contractions, with a pulse duration of 0.25 min. . (Figure 1).

Second Intervention Group: The Patient Controlled Analgesia infusion was started right after the surgery. 4 electrodes were placed at the ST25, P6, ST36, and LI4 acupuncture points of the patients at the 30th minute and 2, 18, 22, 42, and 46th hours after the surgery and electrical stimulation was implemented at varying frequencies of 2-100 Hz for 30 minutes, at a maximum current intensity of 12 milliamperes that would not bother the patient or create muscle contractions, with a pulse duration of 0.25 min. (Figure 2).

Control Group: The Patient Controlled Analgesia infusion was started right after the surgery. No intervention was performed to the patients in the control group. The data of the patients were recorded at the post-operative 30th minute and 2, 18, 22, 42, and 46th hours. The flow chart of the study is shown in Figure 3.

The TENS device used in this study was a dual channel nerve stimulator. This device had 7 preset pain programs and 3 special programs. The program and the amplitude could be set individually for each channel. The electrodes of the device were 4x4 cm in size with 4 pieces in total. The electrodes were placed 2-3 cm lateral to the incision area and at the relevant acupuncture points. The current intensity was manually set according to the patient's tolerance.

Measurements

Baseline measurements

Preoperative measurements: The patients' age, gender, height, weight, diagnosis, history of a chronic sleep disorder and ASA class data were recorded. Pulmonary functions (PEF, FVC), vital signs, respiratory rate, saturation and pain level data were also recorded.

Outcome measurements

Intraoperative measurement: All patients received general anesthesia with the same protocol. The patients were observed during the surgical procedure and data such as incision length, duration of anesthesia, duration of surgery and number of drains were recorded.

Postoperative measurements: The medical findings of all patients after the surgical procedure were recorded.

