Pain: VAS with a range of 1-10 points was used while the pain levels of all patients were evaluated. Pain levels of all patients were evaluated at rest.

Analgesic drug consumption: All patients were administered IV Contramal infusion with PCA for the first 48 hours. Dexketoprofen Trametamol vial IV and/or 50 mg. Pethidine HCl IM was used as the rescue analgesic.

Nausea severity: VAS with a range of 1-10 points was used while evaluating the nausea severity of all patients .

Vomiting: The number of times the patients vomited was recorded.

Antiemetic drug consumption: The antiemetic drug amount administered to the patients was recorded in mg.

Pulmonary function tests: The pulmonary functions of the patients were evaluated with a portable spirometer. PEF and FVC values were recorded. The measurement of respiratory functions was performed with the patient wrapping the disposable mouthpiece well with the lips during the measurement. The patient was asked to breathe deeply and exhale suddenly and quickly. This process was repeated three times and the best performance was taken as the base value.

Sample size: The software package G-power 3.1.3. was used to conduct a prior power analysis to calculate the number of participants required. Sixteen participants were required to detect an effect size of 1.4 at 80% power. The alpha level used to define significance was 0.05.

Blinding: Because the patients and data collector were aware they were implementation electrical stimulation or not, there was no blinding to the study.

Data collection: Data collection was started on the day before the patients underwent surgery and finished on the 2nd day after surgery.

Preoperative data collection: The characteristics of the patients and ASA classifications, vital signs and respiratory functions were evaluated one day prior to the surgery.

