After the data were transferred to the SPSS database, error controls were performed. Their compliance with a normal distribution was evaluated with Kolmogorov Smirnov test. The data determined were mean \pm standard deviation ($X \pm SS$), median and minimum-maximum (min-max) for the variables determined by the measurement and number (n) and percent (%) for the variables determined by counting. Since the variables determined by counting did not comply with a normal distribution, the difference between the three groups was evaluated by the Chi square test. The one-way ANOVA test was used to investigate the difference between the three groups regarding the measured values for values complying with normal distribution and the Kruskal-Wallis test was used for the values that did not comply with a normal distribution. The Bonferroni correction was implemented to determine the source of the difference in group comparisons. The Mann-Whitney U test was used to investigate the difference between two groups of variables. A p value <0.05 was accepted as statistically significant. The Paired Sample T Test was used for values complying with a normal distribution and the Wilcoxon Test was used for values not complying with a normal distribution when comparing the values of patients in the same group before and after the implementation.

Ethical consideration: Written permission and approval was obtained from the Gülhane Military Medical Academy's Head of Clinical Studies Ethics Committee before the study started. Physicians and nurses working at the Gülhane Military Medical Academy, General Surgery Clinic, Post-Operative Care Unit and Post-Anesthesia Care Unit within the Anesthesiology and Reanimation Clinic were informed of the study and verbal approval was obtained.

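### The three-group comparison adjusts for nothing, although diagnosis and preoperative values are recorded before surgery; prespecified adjustment would be a cheap gain if they are prognostic

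*Combined protocol and SAP*

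**What the plan says.** The Data analysis section compares measured values across the arms by group alone: "The one-way ANOVA test was used to investigate the difference between the three groups regarding the measured values" when they look normal, and "the Kruskal-Wallis test was used for the values that did not comply with a normal distribution". Pairs are then separated: "The Bonferroni correction was implemented to determine the source of the difference in group comparisons". Mann-Whitney is named for two-group comparisons and chi-square for counts. No covariate, ANCOVA or regression appears.

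The Inclusion criteria admit patients scheduled for midline surgery "for a diagnosis of stomach or colorectal cancer". The Randomization section describes a block list for three groups and names no stratification factor. Under Baseline measurements, diagnosis, pulmonary function (PEF, FVC), vital signs, respiratory rate, saturation and pain are recorded preoperatively. During surgery, "data such as incision length, duration of anesthesia, duration of surgery and number of drains were recorded". The first stimulation comes 30 minutes after surgery.

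On size, the plan says "Sixteen participants were required to detect an effect size of 1.4 at 80% power", without saying whether 16 is a total or a number per arm.

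**The concern.** The two diagnoses may differ in postoperative pain and drug use, and the difference is handled neither by design nor by analysis. Some outcomes, including pain, PEF and FVC, also have a preoperative value that no between-group test uses. If these variables predict outcome, an analysis that ignores them has wider intervals than the collected data would allow.

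In small arms the diagnosis mix can also differ noticeably by chance. A reader could then not tell how much of an observed difference reflects that mix, and the plan leaves the choice of whether to adjust open until the imbalance has been seen.

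**Working it through.** **1. The plan's own figure.** Inputs from the Sample size paragraph: effect size 1.4 (read as a standardized mean difference), 80% power, alpha 0.05, answer 16. Sidedness and test family are not given. A one-sided two-sample t test needs 8 per arm (power 0.845; 7 per arm gives 0.795), so 8 + 8 = 16. The two-sided version needs 10 per arm, or 20 in two arms. The stated 16 is therefore reproduced exactly as a one-sided, two-group total. That leaves the size of a three-arm trial unclear. The main calculations below **assume 16 per arm (48 in all)**; smaller readings are shown beside them.

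**2. Chance imbalance in diagnosis.** Blocks balance numbers per arm, not diagnosis. Treat the count of one diagnosis in each arm as an independent Binomial(16, p) and find P(largest − smallest ≥ 4), a gap of 25 percentage points between some pair of arms. The diagnosis mix p is assumed.

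| Patients per arm | 50:50 mix | 30:70 mix |
|---|---|---|
| 16 (gap of at least 4) | 43% | 36% |
| 8 (gap of at least 2) | 73% | 68% |

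**3. What such a gap would do.** Suppose, as an illustration, that diagnosis explains 5% of outcome variance at a 50:50 mix. The difference δ between diagnoses satisfies δ² × 0.25 = 0.05, so δ = 0.447 SD. A 25-point gap shifts a contrast by 0.25 × 0.447 = 0.11 SD. The standard error of a contrast is √(2/16) = 0.354 SD.

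**4. Power with and without adjustment.** Two-sided alpha is 0.05/3 per contrast. For q covariates that together explain a share R² of variance:

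- variance of a contrast = (2/16) × (1 − R²) × (N − 4)/(N − 4 − q), where the last factor is the cost of estimating the covariates;
- error df = N − 3 − q.

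Unadjusted, at 1.0 SD: noncentrality 1/0.354 = 2.828, df 45, critical t 2.487, power 63.5%.

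Worked case, q = 1 and R² = 0.2: variance factor 0.8 × 44/43 = 0.819; standard error 0.354 × √0.819 = 0.320; noncentrality 3.126; df 44; critical t 2.489; power 74%.

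| Power at 1.0 SD, 16 per arm (unadjusted 63.5%) | R² = 0 | 0.1 | 0.2 | 0.3 |
|---|---|---|---|---|
| One covariate | 62% | 68% | 74% | 80% |
| Two covariates | 61% | 66% | 72% | 79% |

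R² is not in the documents; the range is an assumption. At the planned 1.4 SD, unadjusted power is already 92.5%; two covariates at R² = 0.1 make it 94%.

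**5. When adjustment costs precision.** The ratio of interval widths (adjusted to unadjusted, 95% intervals) is √[(1 − R²)(N − 4)/(N − 4 − q)] times the ratio of t quantiles. With two covariates:

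| Total N | Width ratio at R² = 0 | 0.1 | 0.2 | 0.3 | Break-even R² |
|---|---|---|---|---|---|
| 48 | 1.025 | 0.972 | 0.917 | 0.857 | about 0.05 |
| 24 | 1.061 | 1.006 | 0.949 | 0.888 | about 0.11 |
| 16 | 1.116 | 1.059 | 0.998 | 0.934 | about 0.20 |

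With one covariate the break-even values are about 0.02, 0.06 and 0.10.

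**6. Validity.** In simulations at N = 16 and N = 48 with R² from 0 to 0.3 (5,000 runs per setting), the unadjusted test rejected a true null in 4.3% to 5.5% of runs.

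**The case against.** The strongest reply is that a one-way comparison is a legitimate analysis of a randomized trial. This stands. Randomization makes the comparison unbiased on average, the standard error already allows for chance imbalance, and the simulations show the nominal error rate. A reader might infer that the unadjusted p values are invalid or the estimates biased; nothing in the documents supports that.

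A second reply is that precision is lost only if the covariates predict outcome, and the plan gives no such figure. This also stands. A reader might conclude that the plan certainly wastes power; the tables show a gain, no change or a small loss, depending on R² and on what 16 means. The shift in step 3 is also well inside one standard error.

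A third tempting reading is that incision length is an obvious baseline covariate because it is recorded before stimulation starts. Being recorded before stimulation does not make it a pre-randomization measurement. The plan does not say when allocation took place, eligibility is assessed the day before surgery, and the Blinding paragraph says that the trial is not blinded. If allocation was made and known before surgery, incision length is a post-randomization measurement. Nor should the two diagnoses be read as two defined operations: the plan specifies diagnoses, with a midline incision in all patients.

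What the replies do not remove is that diagnosis and the preoperative values are free of this timing problem, are already collected, and go unused in the between-group tests.

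**Conclusion.** This is a cheap improvement to the plan, not an error in it. At 16 per arm, one covariate moves power for a 1.0 SD Bonferroni contrast by between −1 and +16 percentage points as R² goes from 0 to 0.3; two covariates move it by between −3 and +15. The practical gain is smaller at the planned 1.4 SD, where power is already high. A gap in diagnosis of at least 4 of 16 between some pair of arms is quite likely (36% to 43%), though its effect on the estimates depends on how prognostic diagnosis is.

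These figures rest on equal arms of 16, two-sided testing, an assumed diagnosis mix and an assumed R². If the trial has 8 per arm or 16 patients in all, imbalance becomes more likely, but adjustment also needs a stronger covariate to pay for itself.

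**What to change.** In the Data analysis section, replace the one-way comparison as the main analysis of measured outcomes by a linear model with group, diagnosis (stomach or colorectal) and the preoperative value of the same outcome where one is recorded. Pain, PEF, FVC, vital signs and saturation have such a value. Analgesic consumption has none listed, so its model would contain group and diagnosis only. Where ranks are used, fit the same model to the ranks. Keep the Bonferroni correction for the pairwise contrasts.

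State that these covariates are used whatever imbalance is observed, and report the one-way test as a sensitivity analysis. State when allocation took place, and add incision length only if that was after surgery or the allocation stayed concealed until surgery ended.

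The cost is a few sentences and one error degree of freedom per covariate (45 falls to 44 or 43 at 48 patients), with no new data. The downside is slightly wider intervals if the covariates explain little: with two covariates, below an R² of about 5% at 48 patients, 11% at 24 and 20% at 16. If the arms prove smaller than 16, diagnosis alone is the more cautious choice.

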Randomization

To determine the groups, randomization was performed with a web-based randomization system with the help of a computer by researchers. A block randomization list was obtained for 3 groups. TENS was implemented to the incision circumference of the patients in the first group and to the acupuncture points of the patients in the second group with no treatment being implemented to the control group.

The interventions

The standard anesthesia protocol was implemented to all patients suitable for the study. All of the patients included in the study were administered 2 mg midazolam IV 5 minutes before the operation as premedication, after the peripheral vein was accessed. Once the ECG, noninvasive blood pressure, and pulse oximeter monitorization was started, preoxygenization was provided and anesthesia induction conducted intravenously with propofol 2-2.5 mg /kg, rocuronium bromide 0.6 mg /kg, and fentanyl 2 mcg /kg. This was followed by oral tracheal intubation 90 seconds after 100% O₂ at 4 l/min was started. After endotracheal intubation, the inhalation agent desflurane was set at 6% concentration. All patients were administered 0.2 mg/kg rocuronium bromide IV at 30-minute intervals and IV remifentanil was adjusted to 0.25 mcg/kg/min. All patients were administered intraoperative ranitidine HCl 20 mg and metoclopramide 10 mg. After the last skin suture was placed, the inhalation agent and remifentanil infusion were terminated. Once spontaneous breathing started, the muscle relaxant agent was antagonized (neostigmin 0.05 mg/kg, atropine 0.015 mg/kg) and the patient was extubated when spontaneous breathing and adequate muscle strength were present.

A standard analgesia protocol for post-operative pain control was used in all patients included in the study. The Patient Controlled Analgesia infusion was administered to the patients for 48 hours. The patients were provided a total of 500 mg Tramadol HCl Patient Controlled Analgesia infusion intravenously (IV) at a concentration of 5 mg/ml, an infusion dose of 5 mg/hr, a bolus dose of 20 mg, and a 150 mg per 4 hour limit with a 30 minute lock-in time. Dexketoprofen Trometamol vial IV and/or 50 mg Pethidine HCl IM were used as rescue analgesic drugs.

A standard antiemetic protocol was used for all patients after surgery. If they had nausea, 4 mg/2 ml ondansetron was administered intravenously.

First Intervention Group: The Patient Controlled Analgesia infusion was started right after the

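### With exactly three groups, Bonferroni after the three-group test is valid but stricter than needed; a closed test would be a cheap gain in power

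*Combined protocol and SAP*

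**What the plan says.** Under Randomization, "A block randomization list was obtained for 3 groups": stimulation around the incision (TENS), stimulation at acupuncture points (TAES), and control. That gives three pairwise contrasts.

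Under Data analysis, the arms are first compared together. For normal data, "The one-way ANOVA test was used to investigate the difference between the three groups"; otherwise, "the Kruskal-Wallis test was used for the values that did not comply with a normal distribution". Then: "The Bonferroni correction was implemented to determine the source of the difference in group comparisons". Next: "The Mann-Whitney U test was used to investigate the difference between two groups of variables". The threshold is "A p value <0.05 was accepted as statistically significant".

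Under Sample size, "Sixteen participants were required to detect an effect size of 1.4 at 80% power", and "The alpha level used to define significance was 0.05".

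The plan does not state the Bonferroni divisor, whether pairwise tests depend on a significant three-group test, whether tests are one- or two-sided, or whether sixteen is per arm or in total. It names no step-down or closed procedure, and no adjustment across the six pain times or the two primary outcomes (pain and analgesic consumption).

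**The concern.** The pairwise contrasts answer the trial's question: each method against control, and the two methods against each other. The plan already screens with a 5% three-group test. A further division of alpha by three is one way to locate the difference, but with three groups it is more than 5% family-wise control requires. The sample size makes no visible allowance for that division, so each contrast may have less power than the 80% the plan aims for. At stake is efficiency in a small trial. The validity of a positive finding is not in question.

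**Working it through.** **Inputs.** Three arms, alpha 0.05, effect size 1.4, 80% power and 16 participants come from the document. Assumed, because they are not stated: the effect size is a standardised mean difference (SD = 1), allocation is 1:1:1 with no dropout, tests are two-sided, and the Bonferroni divisor is 3, so 0.05/3 = 0.0167 per pair.

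**1. The plan's own figure.** For a two-sample t-test, power comes from the noncentral t with 2n − 2 degrees of freedom and noncentrality d√(n/2).
- One-sided, n = 8 per arm: 1.4 × √4 = 2.80, power 84.5%. With n = 7: 1.4 × √3.5 = 2.62, power 79.5%. So 8 per arm, or 16 in two arms, matches exactly.
- Two-sided: 9 per arm gives 79.6%, so 10 per arm are needed. With 16 per arm, power is 96.9%.
- Three-group ANOVA: 24 in total for f = 0.7, or 9 for f = 1.4.

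Sixteen thus reproduces only as a two-arm total. Because the text does not settle this, several arm sizes are used below.

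**2. The logic.** If any two of the three pairwise nulls hold, all three arms are equal. The only intersection hypothesis is therefore the global null, which the three-group test already tests at 5%. Consider the rule: declare a pair only if the three-group test and that pair are both significant at 0.05.
- All arms equal: any false claim requires a false three-group result, at most 5%.
- Exactly one pair equal: the only possible false claim is that pair, tested at 5%.
- Exactly two pairs equal: impossible.

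This is a full closed test, and all three contrasts stay testable.

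**3. Family-wise error by simulation** (100,000 to 200,000 trials per scenario for ANOVA with pooled-variance t-tests, 20,000 for rank tests).

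| Truth | Three-group test, then 0.05/3 | Closed test |
|---|---|---|
| All arms equal, ANOVA | about 4.2% | 5.0% |
| One arm differs by 1.4, ANOVA | 1.6–1.7% | 4.9–5.0% |
| Rank version, all these cases | 1.4–3.7% | 4.5–4.9% |

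Using the three-group test as a gate for Bonferroni makes little difference: with each pair's own variance at 8 per arm, power is 55% ungated and 54% gated.

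**4. Power per true contrast.** The first six rows have one arm different from the other two. The last four have graded means of 0, 0.7 and 1.4.

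| Per arm | Effect, test | Bonferroni | Closed | Gain |
|---|---|---|---|---|
| 8 | 1.4, ANOVA | 58% | 70% | +12 |
| 8 | 1.4, rank | 49–50% | 64–65% | +15 |
| 10 | 1.4, ANOVA | 72% | 82% | +10 |
| 16 | 1.4, ANOVA | 92.5% | 96.6% | +4 |
| 16 | 1.4, rank | 89% | 95% | +6 |
| 16 | 1.0, ANOVA | 64% | 74% | +10 |
| 16 | graded, largest contrast, ANOVA | 92% | 94% | +1 (before rounding) |
| 16 | graded, half-size contrast, ANOVA | 32% | 49% | +17 |
| 8 | graded, largest contrast, rank | 48% | 58% | +10 |
| 8 | graded, half-size contrast, rank | 11% | 23% | +12 |

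Holm falls between: 62% in the first row and 67% in the sixth. In the sixth row, power to detect both true contrasts is 49% with Bonferroni, 55% with Holm and 67% with the closed test. If sixteen were the three-arm total (6/5/5), the gain at 1.4 would be from 34–37% to 45–49%.

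**5. Unequal variances.** Assume control SD 1 and active-arm SDs 1.5. With the ANOVA's pooled variance, the closed test's false-claim rate for TENS v TAES rises to about 7.6% (Bonferroni about 3%). Using only the two compared groups' variance restores 5%. With equal variances that form costs little: closed-test power at 1.4 is 69% with 8 per arm and 96% with 16.

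**6. Six pain times.** Suppose TENS and TAES are equal and control differs clearly. If the times were independent, the chance of at least one false TENS v TAES claim would be 1 − (1 − 0.0167)^6 = 9.6% with Bonferroni and 1 − 0.95^6 = 26.5% with the closed test. Simulation with control 1.4 SD away gives about 8% v 21% at an assumed between-time correlation of 0.5, and 5–6% v 14% at 0.8.

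**The case against.** Bonferroni after a three-group test is conventional, stated in the plan and valid, so choosing another rule is partly preference. That stands, and it makes this an improvement and not a correction.

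A reader might infer three stronger things, none of which the documents support.
- *That the closed test adds a fixed 10 points.* The stated effect is 1.4 and the number per arm is unclear. With 16 per arm at 1.4 the gain is about 4 to 6 points, and Bonferroni already gives about 90%, so the contrasts would not be underpowered on that reading.
- *That the Bonferroni step gives no protection.* It lowers the false-claim rate for a single equal pair from about 5% to 1.7%. It is unnecessary for the nominal 5%, but it is not inert.
- *That the change is free.* With six pain times and two primary outcomes unadjusted, the slack in Bonferroni incidentally absorbs some of that multiplicity. Removing it raises the chance of a false TENS v TAES claim over the six times from about 8% to 21% at correlation 0.5.

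The equal-variance objection also stands for pooled-variance pairwise tests. It is met by basing each pairwise test on its own two groups. Finally, Bonferroni has simple simultaneous confidence intervals and the closed test has none that match it.

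**Conclusion.** This is a cheap improvement. The plan's rule is valid; it is stricter than needed to hold 5% family-wise error among three arms for one outcome at one time. The gain is worth having if the arms are small (about 10 to 12 points at 8 to 10 per arm with effect 1.4) or if the effect is nearer 1.0 SD (about 10 points at 16 per arm). It is modest at 16 per arm with effect 1.4. Across contrasts in graded arms it runs from about 1 to 17 points.

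These figures assume normal data with equal variances, equal arms, no dropout, two-sided tests and three comparisons. The 5% guarantee also requires that the three-group test be a mandatory gate. Neither rule controls error across pain times or across the two primary outcomes.

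**What to change.** Replace the Bonferroni sentence under Data analysis with:

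*A pairwise difference is declared only when the three-group test and that pairwise test are both significant at 0.05 (closed test for three groups); each pairwise test uses only the data of its two groups (two-sample t-test with its own variance, or Mann-Whitney U).*

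If a rule without a gate is preferred, use Holm, which never rejects less than Bonferroni. State the number per arm and the sidedness, so that the power of each contrast can be read from the plan.

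Handle multiplicity over times and outcomes separately, for example by naming one primary pain measure. This should accompany the change, because the closed test leaves less slack.

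The cost is one sentence, with no extra patients and essentially the tests already planned. Ordinary 95% confidence intervals would be reported in place of simultaneous ones. The text is written in the past tense; if results are already known, keep the Bonferroni analysis as planned and label the closed-test analysis post hoc.

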Postoperative data collection: The medical information of the patients was recorded within the initial 48 hours after the surgery. Vital signs, respiratory functions, pain levels, nausea severity, vomiting status, dizziness status, analgesic and antiemetic drug consumption of all patients included in the study were recorded. Vital signs and pain levels of the patients in the control group were evaluated at the post-operative 30th min. and 2,18,22,42, and 46th hours. Vital findings and pain levels of the patients who were included in the intervention groups before and 30 minutes after the implementation were evaluated. All evaluations of the patients were performed during bed rest. Nausea levels, vomiting status and dizziness status of the patients were evaluated at the periods of 0-6, 6-24, and 24-48 hours. Analgesic and antiemetic drug consumption of the patients was

evaluated at the periods of 0-24 and 24-48 hours. Respiratory function evaluations of the patients were performed at the 24th and 48th hours.

Data analysis:

The data obtained from this study were evaluated by using the Statistical Package for the Social Sciences (SPSS, Inc., Chicago, IL, USA) 22.0 software program.

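### Two primary outcomes have no fixed time, window, summary or success rule, so nothing controls error across six pain times, two consumption windows and two primaries

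*Combined protocol and SAP*

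**What the plan says.** All references are to the Combined protocol and SAP.

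- **Opening paragraph:** "The primary outcome measures were the effects of TENS and TAES on pain and analgesic drug consumption". The two are not ranked, and the plan does not say whether one or both must succeed.
- **Postoperative data collection, control arm:** "Vital signs and pain levels of the patients in the control group were evaluated at the post-operative 30th min. and 2,18,22,42, and 46th hours". This is one reading at each of six times, and the Control Group paragraph gives the same schedule.
- **Postoperative data collection, active arms:** "Vital findings and pain levels of the patients who were included in the intervention groups before and 30 minutes after the implementation were evaluated". Sessions start at the same nominal times as the control readings. The First Intervention Group paragraph begins: "4 electrodes were placed 2-3 cm lateral to the incision of the patients at the 30th minute".
- **Consumption:** "evaluated at the periods of 0-24 and 24-48 hours". It comprises PCA tramadol plus rescue: "Dexketoprofen Trometamol vial IV and/or 50 mg Pethidine HCl IM were used as rescue analgesic drugs". No total or combination rule is given.
- **Data analysis:** measured values are compared across the three groups by one-way ANOVA or Kruskal-Wallis, with Bonferroni to locate a group difference. Before and after values within a group are compared by paired t or Wilcoxon tests. The threshold is "A p value <0.05 was accepted as statistically significant". There is no repeated-measures model and no summary over time.

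**The concern.** The 0.05 level belongs to each test, not to the primary claim. The plan allows at least eight three-group comparisons on primary outcomes (six pain times and two windows) and does not say which of them carry the conclusion. A reader of the results could not tell whether a significant 18-hour pain difference was the planned test or one of several.

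The pain contrast is open as well. The Data analysis section gives the paired active-arm readings a use, but only within an arm. Against control there are two candidates, and they answer different questions. The trial is unblinded, so a choice made after seeing the data would be hard to defend.

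**Working it through.** **Inputs from the documents.** Three arms; two primaries; six pain times; two consumption windows; 0.05 per test; six sessions of 30 minutes.

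**Arm size.** The Sample size section gives 16 participants for effect size 1.4, 80% power and alpha 0.05. It does not say per arm or in total, or one- or two-sided. A two-group one-sided t-test reproduces 16 as a total: 8 per group gives 84.5% power and 7 gives 79.5%. Sixteen per group would give 96.9% two-sided. Per-arm size is therefore an assumption below.

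**Step 1: bound under independence.** The chance of at least one p<0.05 among k true nulls is 1 − 0.95^k.
- Six pain times: 1 − 0.95^6 = 26.5%
- Two windows: 1 − 0.95^2 = 9.8%
- All eight: 1 − 0.95^8 = 33.7%

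**Step 2: correlated outcomes.** The documents give no correlations, so a range was simulated: normal data, global null, 16 per arm, eight ANOVAs, each rejecting when F exceeds the 95th percentile of F(2, 3n − 3), 50,000 runs.

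| Correlation within / between outcomes | Any p<0.05 |
|---|---|
| 0 / 0 | 33.6% |
| 0.5 / 0.2 | 28.3% |
| 0.7 / 0.2 | 24.0% |
| 0.9 / 0.2 | 17.5% |
| 0.9 / 0.8 | 14.2% |
| 0.9 / 0.9 | 12.6% (12.4% on a repeat) |
| 0.95 / 0.95 | 10.1% |

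At 0.7 / 0.2, 6 per arm gives 24.9% and 30 per arm 23.6%, so arm size hardly matters. Kruskal-Wallis at 16 per arm gives 27.3% (0.5 / 0.2), 14.2% (0.9 / 0.8) and 10.0% (0.95 / 0.95).

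**Step 3: which active-arm reading.** Sessions start at 0.5, 2, 18, 22, 42 and 46 h and end half an hour later.
- The before-session reading matches the control's nominal time. At 0.5 h it precedes any stimulation. At the other five times the gap since the previous session ended is 2 − 1 = 1 h, 18 − 2.5 = 15.5 h, 22 − 18.5 = 3.5 h, 42 − 22.5 = 19.5 h and 46 − 42.5 = 3.5 h. It therefore measures carry-over only.
- The after-session reading captures the immediate effect. It falls 30 minutes after the control's nominal time if counted from session start, or 30 + 30 = 60 if counted from session end.

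**Step 4: error under a 0.025 split.** Each primary has one value per patient. Its overall test is at 0.025 and its pairs, tested only if that is significant, at 0.025/3 = 0.0083. Within one primary, either all three arms are equal (false claim at most 2.5%) or at most one pair is null (at most 0.83%). The two primaries together give at most 2.5% + 2.5% = 5%. In simulation the split gave 4.0–4.9% under the global null, and 3.0–3.4% with a pain effect and null consumption. Holm followed by pairs at the level it assigns gave 5.2–5.8% in the latter case.

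**Step 5: power of a five-reading pain mean (2–46 h).** Assume 1.4 SD in one active arm at k of five readings, with correlation ρ. The standardised shift is δ = 1.4(k/5)/√((1 + 4ρ)/5), and the ANOVA noncentrality is nδ² × 2/3. For ρ = 0.5, 0.7, 0.9, δ = 1.81, 1.61, 1.46 when k = 5 and 0.72, 0.64, 0.58 when k = 2.

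| Effect at | n per arm | Overall test at 0.025 | Also active vs control at 0.0083 |
|---|---|---|---|
| 5 readings | 16 | 97.7–99.9% | 89–98% |
| 5 readings | 8 | 71–89% | 46–69% |
| 5 readings | 5 | 41–61% | not tabulated |
| 2 readings | 16 | 26–40% | 13–23% |

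**The case against.** The strongest reply is that the plan never says one significant result makes the trial positive. That is correct. A reader might infer an any-one-wins rule, but no sentence states it, so the Step 2 figures illustrate an unexcluded reading and are not the trial's error rate. The opening paragraph's wording could equally mean that both primaries must succeed. No split between them would then be needed, but the choice among times, windows and readings would stay open.

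Bonferroni is in the plan, but its stated purpose is locating group differences. It does not extend to times, windows or outcomes.

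Three other strong readings fail:
- **That active-arm pain is not recorded.** It is, and the paired tests use it. Only its role against control is unstated.
- **That both active readings would be tested against control.** No section describes this, so no error rate is attached to it.
- **That the past tense shows the outcomes were already examined.** The whole document is in the past tense yet dated May 1, 2015, and the remark on non-normality concerns count variables. Tense settles nothing.

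**Conclusion.** The concern holds as a gap in specification. The documents fix neither the primary comparison nor its error rate, and no redaction or missing figure accounts for this. If each time and window were tested and any p<0.05 counted, the risk would be about 12–28% at within-outcome correlations of 0.5–0.9, about 10% at a common 0.95 and 34% under independence. It exceeds 5% in every scenario run. These figures rest on assumed correlations and normal data, and are insensitive to arm size. The power figures do depend on arm size, which the documents leave unclear. The matter should be corrected, but it does not make the data unusable.

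**What to change.** Before outcome data are analysed, add to the Data analysis section:

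1. **Pain.** One value per patient: mean resting VAS over stated times, or one arm effect from a repeated-measures model. Name the active-arm reading and its limitation from Step 3: carry-over only (before-session) or a 30–60 minute timing mismatch (after-session). If the before-session reading is chosen, average 2–46 h and use the 30-minute reading as a covariate.
2. **Consumption.** One 0–48 h value per patient, for example total PCA tramadol with rescue use reported alongside. Disclose that the total includes the stated background infusion (5 mg/hr × 48 h = 240 mg if run throughout) and can miss a shift to rescue drugs. Any rule combining drugs should be pre-stated and its weighting acknowledged as an assumption.
3. **Success rule.** State whether either or both primaries must succeed. If either suffices, test each overall three-group comparison at 0.025 and, only if significant, its three pairs at 0.025/3.
4. **Reporting.** Present single times and windows as descriptive. If outcome data have already been examined, label the choice post hoc.

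**Cost.** No new data. Single-time results can no longer be claimed as primary. Averaging dilutes a short-lived effect, and power is weak if arms are small, as Step 5 shows. The fixed split costs slightly more power than Holm, which is an alternative only if the two overall tests are the sole primary claims.
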